**LIST OF ABBREVIATIONS**

IG	Intervention group
CG/ WLC	(Waitlist-) Control group
ITT	Intention-to-treat
PP	Per-Protocol
ANCOVA	ANalysis of COVAriance
ANOVA	ANalysis Of VAriance
SD	Standard Deviation
SE	Standard Error

## 1. STUDY OBJECTIVES

### 1.1. PRIMARY OBJECTIVE

The goal of this clinical trial is to examine the efficacy of a newly developed online resilience intervention "resiLIR Health Care Professionals" for Health Care professionals and foster resilience in the targeted population.

### 1.2. SECONDARY OBJECTIVES

Secondary objectives are to find out whether the intervention is effective in increasing the addressed health-related and resilience factors (e.g., optimism) as well as decreasing self-evaluations of psychopathological indicators (e.g., depression, anxiety) in healthcare professionals. Also, the study investigates whether different interventions are effective in changing state-measures of health-related self-evaluations.

Another objective is to investigate these effects in the long term (up to one-year post-intervention).

Additionally, feasibility and usability of the intervention and the newly developed platform resiLIR will be investigated.

Further objectives are to examine exploratorily the influence of the intervention on other resilience-related outcomes, mental health literacy, health seeking behaviour and stigma against mental illness and to conduct network analyses.

## 2. BACKGROUND/INTRODUCTION

Acute and chronic stress in everyday life plays an essential role in the onset and development of several physical and mental health conditions. The ability to maintain or return to mental health during stress exposure is characterized as resilience. Especially the COVID-19 pandemic emphasized the role of resilience for mental health and pointed to the importance of easily accessible and flexible interventions to improve resilience for vulnerable groups such as healthcare professionals.

### 2.1. STUDY DESIGN

Randomized Controlled Trial with 240 participants working as healthcare professionals (120 in intervention, 120 in waitlist control group), monocentric study, duration: 14 months, study design chosen to evaluate long-term effects of our training)

### 2.2. TREATMENT GROUPS

Treatment: Participants in the intervention group will gain access to the 6-week online resilience intervention "resiLIR Healthcare Professionals".

The waitlist control group will receive access to the intervention after the first follow-up assessment (3 months post-intervention).

Randomisation process: Stratified randomization is used, with age and gender as influencing factors. Randomization is performed using randomized numbers generated with Microsoft Excel. Due to the nature of the intervention, no blinding and subject replacements are planned.

Subject replacement: not applicable.

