### 2.5. SAMPLE SIZE

Previous studies from our research groups have shown a medium to large effect size for the stressor reactivity score as a primary outcome measure in online intervention studies for resilience (AG [name], unpublished). Because a large effect size was found only in a particularly stressed population, which is not expected in the sample addressed here, we assume a medium effect here (Hedges'  $g = .50$ ). Therefore, the sample size design was calculated with a medium effect size, a significance level of 0.05 and a power of 0.90 using G\*Power (Faul et al., 2007). This results in a required sample size of  $n = 74$  per group ( $N = 146$ ). As there are high dropout rates for online interventions (van Ballegooijen et al., 2014) we decided to recruit  $n = 120$  individuals per group. This number is based on an assumed dropout rate of 40%.

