#### HANDLING OF MISSING DATA

- On the one hand, the data will be analysed according to the "intention-to-treat" principle, with missing values being replaced using appropriate imputation methods.
- On the other hand, the results will be reported as "per-protocol" analysis, in which only those cases are considered that have gone through the study procedure as defined by protocol. We consider the intervention to be completed for participants who, in addition to the theory modules, completed at least 50% of the weekly interventions and the daily training interventions. To note, a maximum of 4 weekly interventions with 6 daily interventions can be reached. In the per-protocol analysis, only these participants will be included. To control for influences of compliance, usage of intervention will be examined as covariate in an exploratory analysis.

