### 5.2. PRIMARY AND SECONDARY DATA ANALYSES

In primary and secondary data analyses, all stated hypotheses will be tested. In all analyses an error probability of  $\alpha = .05$  will be set a priori for interference statistics calculations. In cases of multiple testing,  $\alpha$  will be adjusted accordingly. In addition to statistical significance, descriptive statistics and effect sizes (e.g., Cohen's  $d$ ) will be reported. Publication of results will follow CONSORT guidelines for transparent reporting of randomized trials.

Cronbach's  $\alpha$  and McDonald's  $\omega$  will be calculated as measure of reliability of the respective questionnaires.

Before data analysis, assumptions of statistical methods (e.g., variance of homogeneity, normal distribution) will be tested with suitable procedures (e.g., Levene-tests, Box's M, histograms, QQ-plots, and Shapiro-Wilk-Test). Zero-order correlations between study variables will be reported. Non-parametric correlation calculation will be based on results of (non-)normality, etc. Variables will be standardized where applicable.

The analysis plan for H1 to H11 is as follows:

- Differences between study groups in primary and secondary outcomes before ( $t_0$ ) and after the intervention ( $t_2$ ) and at the time of the first follow-up ( $t_3$ ) will be examined using mixed analyses of covariance (ANCOVA), with group (intervention vs. waitlist-control) as a between-subjects factor, time ( $t_0$ ,  $t_2$ ,  $t_3$ ) as a within-subjects factor and pre-measurement ( $t_0$ ) included as a covariate to increase test power. Outcomes will be the primary outcome resilience (measured with SR Score) and the secondary outcomes resilience (measured with BRS), perceived stress, self-care, self-compassion, mindfulness, mental health, depression, anxiety, burnout, and work-life-balance, respectively.
- If applicable, post-hoc  $t$ -tests will be conducted.
- Effect sizes will be calculated for the ANCOVA (i.e.,  $\text{Eta}^2$ ) as well as for between-group differences (i.e., Cohen's  $d$ ) at post-intervention assessment ( $t_2$ ) and the first follow-up assessment ( $t_3$ ). Also, the effect size of the intervention effect will be calculated (i.e., Cohen's  $d$ ).

The analysis plan for H12 is as follows: term effect over the follow-up measurements ( $t_0$  to  $t_5$ ) within the intervention group will be tested using a repeated measures ANOVA.

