### **5.3. EXPLORATORY DATA ANALYSES**

All other outcome measures mentioned above and not directly addressed in the intervention will be evaluated exploratively.

In addition, changes will be examined in correlative network analyses of the variables. Moderator and mediator analyses are intended as exploratory analyses to examine the influence of mediating/moderating variables (e.g., gender, personality, intervention usage, attitudes toward online psychological interventions, coping styles) of the primary correlations.

The intermediate survey ( $t_1$ ) will be exploratively included in the analyses.

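### Randomisation is stratified by age and gender, but the confirmatory H1–H11 model leaves both factors out and gives up a little precision

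*SAP*

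**What the plan says.** On allocation, SAP section 2.2 states: "Stratified randomization is used, with age and gender as influencing factors". It gives no age cut-points and does not say whether allocation is blocked within strata, that is, whether balance is forced.

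On analysis, section 5.2 defines one model for H1 to H11, covering the primary outcome and ten secondary outcomes. It is a mixed ANCOVA "with group (intervention vs. waitlist-control) as a between-subjects factor", with time (t0, t2, t3) as the within-subjects factor. The t0 value is the only covariate, "included as a covariate to increase test power".

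Elsewhere, the two stratification factors have these roles:

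- Section 4.3 lists age and sex among the demographic data.
- Section 5.1 describes demographic variables and tests baseline differences, but plans no adjustment.
- Section 5.1, under missing data, names one further covariate, and only for exploration: "usage of intervention will be examined as covariate in an exploratory analysis".
- Section 5.3 names gender among the examples of exploratory moderators or mediators ("e.g., gender, personality, intervention usage, attitudes toward online psychological interventions, coping styles"). Age is not named there.

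The SAP gives no reason for leaving the stratification factors out of the confirmatory model.

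**The concern.** A factor is normally used to stratify allocation because it is expected to predict outcome, and section 2.2 itself describes age and gender as influential. If they do predict outcome, a model without them has two consequences.

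First, the variance they explain beyond t0 stays in the residual and power is lower than it need be. Section 5.2 gives power as its reason for including t0, and that reason extends to the randomisation factors as far as they are prognostic.

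Second, if balance is forced within strata, the true spread of the group difference is smaller than the unadjusted model assumes. The reported standard error is then slightly too large and the test mildly conservative. If balance is not forced, the standard error is correct and only power is lost.

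One model serves eleven outcomes, so the effect, though small, is repeated across all of them.

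**Working it through.** **Inputs from the SAP.** Allocation is 120 per arm (section 2.1). Assumed dropout is 40%, the effect is 0.50 SD, alpha is 0.05 and target power is 0.90 (section 2.5). Completers per arm: 120 × (1 − 0.40) = 72.

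**Inputs assumed.** The test is two-sided. R² is the share of the variance remaining after t0 that age and gender explain. The SAP gives no figure, so I used 2%, 5% and 10%, with 0 as the floor. The correlation r between t0 and outcome is also not given; I used 0, 0.5 and 0.7. Dropout is taken as random.

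The SAP has no figure of its own on this point to reproduce. Its sample size derivation is a separate matter and is not used here beyond the inputs above.

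**Step 1: standard error without the factors, balance forced.** Balance is imposed on 120 per arm and 72 remain at random, so 40% of the strata's contribution returns as chance imbalance. In units of the residual variance after t0:

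- True variance of the group difference: (2/72)(1 − R² + 0.4R²) = (2/72)(1 − 0.6R²).
- Variance that the unadjusted model estimates: 2/72.
- Ratio of reported to true standard error: 1/√(1 − 0.6R²) = 1.006, 1.015 and 1.031 for R² = 2%, 5% and 10%.

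**Step 2: type I error, balance forced.** 2·P(T > t_crit/√(1 − 0.6R²)) with 142 degrees of freedom gives 0.0486, 0.0466 and 0.0433. Without forced balance the ratio is 1 and type I error is 0.05.

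**Step 3: power with 72 per arm.** This uses the noncentral t distribution with standardised effect 0.5/√(1 − r²) unadjusted and 0.5/√((1 − r²)(1 − R²)) adjusted. Losses are taken from unrounded powers.

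| r | R² | Unadjusted, not forced | Unadjusted, forced | Adjusted | Points lost (forced / not forced) |
|---|---|---|---|---|---|
| 0 | 2% | 0.846 | 0.847 | 0.853 | 0.6 / 0.7 |
| 0 | 5% | 0.846 | 0.850 | 0.864 | 1.4 / 1.7 |
| 0 | 10% | 0.846 | 0.853 | 0.881 | 2.8 / 3.5 |
| 0.5 | 2% | 0.931 | 0.932 | 0.935 | 0.3 / 0.5 |
| 0.5 | 5% | 0.931 | 0.934 | 0.942 | 0.8 / 1.1 |
| 0.5 | 10% | 0.931 | 0.937 | 0.952 | 1.6 / 2.2 |

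At r = 0.7 without forced balance, power is 0.987 unadjusted and 0.988, 0.990 and 0.993 adjusted, a loss of at most 0.6 points.

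**Step 4: simulation.** With 20,000 trials per setting, four equal strata, r = 0.5 and R² = 10%:

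- Forced balance: standard error ratio 1.027; type I error 0.044 unadjusted and 0.049 adjusted; power 0.936 and 0.950.
- No forced balance: standard error ratio 1.00; type I error 0.049 for both; power 0.931 and 0.948.

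At R² = 2% the effect cannot be told from simulation noise.

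**Step 5: no erosion of balance by dropout.** If balance holds among the 144 analysed participants, the conservatism is larger. A second simulation of that case gave type I error of 4.8%, 4.4% and 3.9% for R² = 2%, 5% and 10%, against 5.0% with the factors in the model. The reported standard error at 10% was about 5% too large (0.1670 against a true spread of 0.1592). The direction is the same; the figures in steps 1 and 2 are the more cautious ones because they allow for dropout.

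**The case against.** The strongest reply is that the planned test is valid. There is no bias and no excess type I error, and if balance is not forced, even the standard error is right. The SAP never promises to adjust for the stratification factors, so the criticism rests on good practice and not on an internal contradiction. Describing age and gender as influential in a sentence about allocation is no evidence that they predict the SR score or burnout once t0 is known. All of this stands, and it caps the point at minor.

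The size can also be challenged. Every R² value is assumed, and the largest losses need a t0 correlation of zero, which sits badly with a plan that includes t0 to gain power. The setting is completers only and a single endpoint, whereas the SAP plans an intention-to-treat analysis with imputation over several time points. With full information on 120 per arm and no forced balance, the loss at r = 0.5 shrinks to about 0.1, 0.2 and 0.3 points. The intention-to-treat figure should lie between the two settings, so the table is the pessimistic end. That also stands. It limits the gain but does not show the omission to be the better choice.

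Finally, section 5.2 lists t0 both as a level of the time factor and as the covariate, and adding terms to that model does not cure this. That is correct, but it is a separate issue and has no bearing on whether the stratification factors belong in the model.

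**Conclusion.** The point holds as a minor one. The trial randomises by age and gender and then leaves both out of all eleven confirmatory models without giving a reason.

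For an assumed R² of 2% to 10% and 72 completers per arm, the cost is 0.3 to 2.2 points of power at a t0 correlation of 0.5, up to 3.5 points at zero correlation and at most 0.6 at 0.7. If balance is forced, the standard error is also overstated by 0.6% to 3.1% and type I error falls to between 0.049 and 0.043. The cost is zero if the factors explain nothing beyond t0, and smaller if imputation recovers much of the missing information. The validity of the planned test is not in question.

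**What to change.** In section 5.2, add gender and the age stratum, coded exactly as used in the randomisation, as fixed covariates alongside t0 in the H1–H11 model. Use the same covariates in the group contrasts at t2 and t3. State that this is the single confirmatory model, so that adjusted and unadjusted results cannot later be presented as alternatives. The double role of t0 as time level and covariate should be settled separately, so that this change does not lock it in.

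The cost is one sentence and a few degrees of freedom. Age and sex are already collected, so no new data are needed. The change should be made before the data are analysed.

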### 2.3. STUDY POPULATION

Inclusion criteria:

- Age 18 years or older
- Fluent in German language
- Access to web-enabled devices (tablet/laptop/computer)
- Smartphone with internet access
- Trained and employed as health care professionals
  - We used the following definition of healthcare professionals: „Healthcare professionals are specifically trained, often regulated professions that advise on or provide health services. This includes, amongst others, medical doctors, nurses, physiotherapists, speech therapists, psychotherapists, dentists, medical-technical assistants, geriatric nurses,...”

Exclusion Criteria:

- Acute mental health crisis (e.g., suicidality)
- Psychiatric/psychotherapeutic treatment
- Neurodegenerative disease(s)
- Diagnosis of schizophrenia or other psychotic disorders, bipolar disorder, post-traumatic stress disorder

### 2.4. INTERVENTION

Behavioral intervention delivered via computer/laptop and smartphone

- Weeks 1 and 2 (delivered mainly via computer): Theoretical part on stress, resilience, self-care, and self-compassion
- Weeks 3 to 6 (delivered mainly via smartphone): Training phase of a weekly introduced practical exercise (*weekly training intervention*; topics: reflection on living with ease, self-compassionate body scan, planning of positive activities, self-compassionate letter). This phase additionally includes smartphone reminders to apply the exercises in everyday life (*daily training interventions*).

[figure not shown]
### 2.5. SAMPLE SIZE

Previous studies from our research groups have shown a medium to large effect size for the stressor reactivity score as a primary outcome measure in online intervention studies for resilience (AG [name], unpublished). Because a large effect size was found only in a particularly stressed population, which is not expected in the sample addressed here, we assume a medium effect here (Hedges'  $g = .50$ ). Therefore, the sample size design was calculated with a medium effect size, a significance level of 0.05 and a power of 0.90 using G\*Power (Faul et al., 2007). This results in a required sample size of  $n = 74$  per group ( $N = 146$ ). As there are high dropout rates for online interventions (van Ballegooijen et al., 2014) we decided to recruit  $n = 120$  individuals per group. This number is based on an assumed dropout rate of 40%.

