**4.4. Hypotheses**

1. The intervention will significantly increase resilience, measured with the SR Score, in the intervention group (IG) compared with a waitlist control (WLC) group at  $t_2$  and  $t_3$  compared to  $t_0$ .
2. The intervention will significantly increase resilience, measured with the Brief Resilience Scale, in the intervention group (IG) compared with a waitlist control (WLC) group at  $t_2$  and  $t_3$  compared to  $t_0$ .
3. The intervention will significantly increase self-care in the intervention group (IG) compared with a waitlist control (WLC) group at  $t_2$  and  $t_3$  compared to  $t_0$ .
4. The intervention will significantly increase self-compassion in the intervention group (IG) compared with a waitlist control (WLC) group at  $t_2$  and  $t_3$  compared to  $t_0$ .
5. The intervention will significantly increase mindfulness in the intervention group (IG) compared with a waitlist control (WLC) group at  $t_2$  and  $t_3$  compared to  $t_0$ .
6. The intervention will significantly reduce perceived stress in the intervention group (IG) compared with a waitlist control (WLC) group at  $t_2$  and  $t_3$  compared to  $t_0$ .
7. The intervention will significantly increase mental health in the intervention group (IG) compared with a waitlist control (WLC) group at  $t_2$  and  $t_3$  compared to  $t_0$ .
8. The intervention will significantly reduce depressive symptoms in the intervention group (IG) compared with a waitlist control (WLC) group at  $t_2$  and  $t_3$  compared to  $t_0$ .
9. The intervention will significantly reduce anxiety symptoms in the intervention group (IG) compared with a waitlist control (WLC) group at  $t_2$  and  $t_3$  compared to  $t_0$ .
10. The intervention will significantly reduce burnout symptoms in the intervention group (IG) compared with a waitlist control (WLC) group at  $t_2$  and  $t_3$  compared to  $t_0$ .
11. The intervention will significantly increase work-life-balance in the intervention group (IG) compared with a waitlist control (WLC) group at  $t_2$  and  $t_3$  compared to  $t_0$ .
12. In the intervention group, the intervention will lead to improved resilience by the end of the intervention (at  $t_2$ ) and these improvements should be maintained at the respective follow-ups (at  $t_3$ ,  $t_4$ ,  $t_5$ ; probably to a lesser degree).
13. Self-compassion interventions (weekly intervention and daily training intervention) in the practice modules:

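### SAP section 2.5 is internally inconsistent: 74 per group is 148 in total, not 146, and 120 per group less 40% dropout leaves 72, below either figure (minor)

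*SAP*

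**What the plan says.** Section 2.5 assumes Hedges' g = 0.50 and reports that "the sample size design was calculated with a medium effect size, a significance level of 0.05 and a power of 0.90", using G*Power. It continues "This results in a required sample size of" 74 per group, with N = 146 in brackets. It then sets recruitment at 120 per group and explains: "This number is based on an assumed dropout rate of 40" per cent. Section 2.1 agrees on the recruited total: "Randomized Controlled Trial with 240 participants working as healthcare professionals", 120 in each arm.

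The analysis that this sample serves is in section 5.2. It is a mixed ANCOVA over t0, t2 and t3 "with group (intervention vs. waitlist-control) as a between-subjects factor", and the t0 measurement is "included as a covariate to increase test power". Neither section 2.5 nor section 5.2 states whether tests are one- or two-sided, and no correlation is given. For the intention-to-treat analysis, section 5.1 (handling of missing data) plans for "missing values being replaced using appropriate imputation methods".

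**The concern.** Section 2.5 gives a chain: a requirement per group, a total, a dropout rate and a recruitment number. Two links fail on the section's own figures. The total is not twice the group size, and the number left after dropout is below the number said to be required. Anyone who repeats the arithmetic will find a misstated sample size, and the trial report will inherit it.

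A second matter is context. The stated inputs do not by themselves lead to 73 or 74 per group, so a reader cannot tell from this section which member of the 74/146 pair is the slip. Nor can the claimed 0.90 be checked against the planned ANCOVA.

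**Working it through.** **Inputs from section 2.5:** g = 0.50 (so SD = 1), alpha 0.05, power 0.90, 74 per group, N = 146, 120 recruited per group, dropout 40%. Sections 2.1 and 2.5 give equal allocation. All correlations below are assumptions, because the SAP states none.

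**Step 1. Group size against total.** 2 × 74 = 148, and 146 / 2 = 73. With equal groups, 74 and 146 cannot both be right.

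**Step 2. Recruitment against dropout.**
- 120 × (1 − 0.40) = 72 per group; 240 × 0.60 = 144 in total. This is below 74 and below 73.
- Dropout that 120 can absorb: 1 − 74/120 = 38.3% to keep 74; 1 − 73/120 = 39.2% to keep 73.
- Recruitment needed at 40% dropout: 74/0.60 = 123.3, so 124 per group; 73/0.60 = 121.7, so 122 per group.

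**Step 3. Cost of the gap.** Two-sample t-test (noncentral t) at d = 0.50:

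| n per group | Two-sided power | One-sided power |
|---|---|---|
| 74 | 0.856 | 0.917 |
| 73 | 0.851 | 0.913 |
| 72 | 0.846 | 0.910 |

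From 74 to 72 the loss is 0.010 two-sided and 0.007 one-sided.

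**Step 4. Can the stated figure be reproduced?**
- Two-sample t-test for 0.90: 86 per group two-sided (power 0.903; 85 gives 0.8999), or 70 one-sided (0.903). Neither is 73 or 74.
- Two-sided ANCOVA at one time point with t0 as the single covariate: noncentral F with 1 and N − 3 df, noncentrality N × 0.25² / (1 − r²), where r is the correlation between t0 and the outcome. At r = 0 this needs N = 171, at r = 0.37 N = 148, and at r = 0.38 N = 146.
- Other unstated settings also reach the figure. A repeated-measures between-group F-test gives N = 146 with two measurements correlated at 0.7, and N = 148 with three correlated at 0.8. A one-sided Wilcoxon-Mann-Whitney test (efficiency 3/π) gives 73 per group, N = 146.

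**Step 5. Power at 72 per group, two-sided ANCOVA at one time point** (same formula, N = 144, 141 df): r = 0 gives 0.846; r = 0.2 gives 0.860; r = 0.3 gives 0.878; r = 0.37 gives 0.894; r = 0.38 gives 0.896; r = 0.394 gives 0.900; r = 0.4 gives 0.902.

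**The case against.** The strongest reply is that these are slips of two participants: two in the total, and two per group after dropout. The recruited number, which governs the conduct of the trial, is the same in sections 2.1 and 2.5. Under the ANCOVA settings that do give 148 or 146, 72 per group still has power of 0.894 to 0.896. Moreover, 72 counts completers only, and participants with partial data contribute to the imputed intention-to-treat analysis. All of this stands, and it is why the point is minor. It does not make 74 and 146 compatible, nor does it make 120 less 40% equal to 74, and the section itself ties 120 to that dropout rate.

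It can also be said that the test, sidedness and correlation may be in the protocol, which is not at hand, and that section 2.5 only recaps the design. That stands too, so their absence here is context and not an error in its own right.

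Two stronger readings are tempting. One is that the trial is underpowered, because a two-sided t-test needs 86 per group. The documents do not support this: the planned primary analysis is baseline-adjusted, and an assumed correlation of 0.37 to 0.38 yields the stated total. The other is that the tests must be one-sided, because the hypotheses in section 4.4 are directional ("The intervention will significantly increase resilience, measured with the SR Score"). The SAP never says so, and a one-sided t-test gives 70 per group, not 73 or 74.

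**Conclusion.** The inconsistency holds and needs no assumption: 74 per group is 148, 146 is 73 per group, and 40% dropout from 120 leaves 72. Its size is about one point of power or less. Severity is minor.

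The required number is not shown to be wrong. It cannot be derived from the stated inputs alone, but it may be right under settings that the section does not state. Whether 72 per group delivers 0.90 depends on the contrast and the correlations. For a two-sided, baseline-adjusted comparison at one time point with g = 0.50, it does so if the t0-outcome correlation is about 0.39 or more, and gives 0.86 to 0.88 at 0.2 to 0.3. Nothing in the SAP shows where the true correlation lies.

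**What to change.** Keep 120 per group and amend section 2.5 as follows:
- Replace the 74/146 pair with one consistent pair (74 and 148, or 73 and 146), whichever the G*Power output shows.
- State that 40% dropout from 120 leaves 72 per group, or state the dropout of about 38% that 120 supports if 74 is to be kept.
- Name the G*Power test, the sidedness and any correlation actually used.
- Restate the power at 72 per group for the planned baseline-adjusted primary contrast. If that contrast is at one time point, possible wording is: *With 40% dropout, 120 per group leaves 72 per group. For g = 0.50 at two-sided alpha 0.05, the baseline-adjusted comparison has about 90% power if the t0-outcome correlation is at least about 0.39 (assumption), and 86% to 88% if it is 0.2 to 0.3.* If the contrast pools t2 and t3, give its power instead, with the assumed t2-t3 correlation.

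The cost is a few lines of SAP text and no extra participants. The downside is that the stated power may become slightly less favourable, or will visibly rest on a correlation that the sponsor has to justify.
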